## **Objectives:**

## 1. Primary objective:

Intracranial objective response rate assessed by the investigators using modified RECIST criteria before local treatment in cohort 1 and in cohort 2.

2. Secondary objectives:

- a.Intracranial objective response rate assessed by the investigators using modified RECIST criteria. before local treatment in cohort 2.
- b. Intracranial objective response rate assessed by the investigators using modified RECIST criteria, before local treatment in cohort 1.
- c.The duration of the intracranial response in both cohorts assessed by the investigators using modified RECIST criteria.
- d. The intracranial progression free survival assessed by the investigators using modified RECIST criteria in both cohorts.
- e. Percentage of patients free of intracranial progression according to modified RECIST criteria at 6 (week 24), 12 (week 48) and 24 months (week 96) in both cohorts
- f. Percentage of patients free of extracraneal progression according to RECIST criteria at 6 (week 24), 12 (week 48) and 24 months (week 96) in both cohorts
- g. Overall survival in both cohorts
- h.Percentage of alive patients at 6, 12 and 24 months in both cohorts
- i. Toxicity of the combination until local treatment in both cohorts
  - I. Toxicity of the combination after local treatment in both cohorts
  - II. Quality of life in both cohorts

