#### 2. Secondary objectives:

[figure not shown]
- a. Intracranial objective response rate assessed by the investigators using modified RECIST 1.1 before local treatment in cohort 2.
- b. Intracranial objective response rate assessed by the investigators using modified RECIST 1.1 before local treatment in cohort 1.
- c. The duration of the intracranial response in both cohorts assessed by the investigators using modified RECIST 1.1.
- d. The intracranial progression free survival by modified RECIST in both cohorts
- e. Percentage of patients free of intracranial progression according to modified RECIST at 6 (week 24), 12 (week 48) and 24 months (week 96) in both cohorts.
- f. Percentage of patients free of extracraneal progression according to RECIST 1.1 () at 6 (week 24), 12 (week 48) and 24 months (week 96) in both cohorts.
- g. Overall survival in both cohorts.
- h. Percentage of alive patients at 6, 12 and 24 months in both cohorts.
- i. Toxicity of the combination until local treatment in both cohorts:
  - Toxicity of the combination after local treatment in both cohorts.
  - Quality of life in both cohorts.

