performed within 6 months after database closure expected at 24 months after last patient inclusion, however interim analysis might be performed when analysing other primary variables

Percentage of patients (%) free of extracraneal progression at 6 (week 24), 12 (week 28) and 24 months (week 96): percentage of patients free of progression by RECIST 1.1 at 6 months (week 24), 12 months (week 48) and 24-month (week 96) considering date of inclusion. The final statistical analysis of this endpoint is expected to be performed within 6 months after database closure expected at 24 months after last patient inclusion, however interim analysis might be performed when analysing other primary variables.

**Overall Survival in both cohorts (OS):** OS is calculated as the time from date of inclusion to date of death due to any cause. The final statistical analysis of this endpoint is expected to be performed within 6 months after database closure expected at 24 months after last patient inclusion, however interim analysis might be performed when analysing other primary variables.

Percentage of patients (%) alive at 6, 12 and 24 months in both cohorts: percentage of patients alive at 6 months, 12 month and 24-month considering date of inclusion. The final statistical analysis of this endpoint is expected to be performed within 6 months after database closure expected at 24 months after last patient inclusion, however interim analysis might be performed when analysing other primary variables.

**Toxicity of the combination until local treatment:** Number of patients with adverse events and serious adverse events, changes in laboratory values, vital signs, electrocardiograms (ECGs), LVEF (MUGA (Multigated Acquisition Scan) / echocardiogram) and assessment of physician, dermatological and ocular examinations graded according to the National Cancer Institute (NCI) Common Terminology Criteria for Adverse Events (CTCAE) v 4.03 until local treatment (local treatment D1). It will be studied using descriptive statistics techniques, such as frequency tables and contingency tables. The final statistical analysis of this endpoint is expected to be performed within 6 months after database closure expected at 24 months after last patient inclusion, however interim analysis might be performed when analysing other primary variables.

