**Toxicity of the combination after local treatment:** Number of patients with adverse events and serious adverse events, changes in laboratory values, vital signs, electrocardiograms (ECGs), LVEF (MUGA (Multigated Acquisition Scan) / echocardiogram) and assessment of physician, dermatological and ocular examinations graded according to the National Cancer Institute (NCI) Common Terminology Criteria for Adverse Events (CTCAE) v 4.03 after local treatment (after end of local treatment date). It will be studied using descriptive statistics techniques, such as frequency tables and contingency tables. The final statistical analysis of this endpoint is expected to be performed within 6 months after database closure expected at 24 months after last patient inclusion, however interim analysis might be performed when analysing other primary variables.

**Quality of life:** Change from baseline in the global health status score of the EORTC QLQ-C30. The final statistical analysis of this endpoint is expected to be performed within 6 months after database closure expected at 24 months after last patient inclusion, however interim analysis might be performed when analysing other primary variables.

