#### **5. SAFETY ANALYSIS**

In safety population.

Table 124: Overall safety

Cohort
Adverse Events
No
Yes
AE Grade >=3
No
Yes
Toxicity: AE related to Binimetinib
No
Yes
Toxicity: AE related to Encorafenib
No
Yes
Toxicity: AE related to any treatment
No
Yes
Toxicity: AE related to all treatments
No
Yes
Toxicity grade >=3
No
Yes
Toxicity related to Binimetinib grade >=3
No
Yes
Toxicity related to Encorafenib grade >=3
No No
Yes
Toxicity related to all treatments grade
>=3
No
Yes
SAE
No

Cohort Yes

Table 125: Most frequent Toxicity with 5% threshold

Toxicity	Frequency	Percentage (%)

Table 126: Grade of most frequent toxicities with 5% threshold overall

Toxicity No G-UK G-1 G-2 G-3	G-3 G-4	G-5
10XICITY 140 G-011 G-1 G-2 G-0	<del>0-0</del> <del>0-1</del>	 

Table 127: List of toxicities grade >=3 in all patients

Patient Number Cohort AE CTCAE AE Grade AE Related to					
	Patient Number	Cohort	AE CTCAE	AE Grade	AE Related to

Table 128: Most frequent AEs with 5% threshold

AE	Frequency	Percentage (%)

Table 129: Grade of most frequent AEs with 5% threshold overall

AE	No	G-UK	G-1	G-2	G-3	G-4	G-5

Table 130: List of all SAEs

Patient Cohort	AE CTCAE	AE AE AE CTCAE Other Grad Star e Date	AE t Stop	AE AE Relat SAE	AE Intensity	AE Related
		e Date	Date	ed 5/1		to

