#### 2.2. OS ON ITT ACCORDING TO RADIOTHERAPY

Table 6: Events type OS

Radiotherapy	
Death	
Alive	

1. Pearson's Chi-squared test

Table 7: Median/mean OS (estimated by Kaplan-Meier)

	Median (months)	CI 95%	Mean	CI 95%
No				
Yes				

Table 8: OS estimated survival ratio

os	Events (%, total N)	Patients at risk	% estimated cumulative survival ratio	CI 95%
No				
At 6 months				
At 12				
months				
At 18				
months				
At 24				
months				
Yes				
At 6 months				
At 12				
months				
At 18				
months				
At 24				
months				

Figure 25: Overall survival vs Radiotherapy

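### No SAP safety summary table visible in the available text splits adverse events by local-treatment period, so the two secondary endpoints of toxicity until and after local treatment have no visible summary output

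*Combined protocol and SAP*

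**What the plan says.** The Synopsis lists "Toxicity of the combination until local treatment in both cohorts" among the secondary objectives. Section 4.2 lists its counterpart, "Toxicity of the combination after local treatment in both cohorts".

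Section 10.2 turns these into two endpoints with separate windows. The first runs "until local treatment (local treatment D1"). The second covers toxicity "after local treatment (after end of local treatment date"). Each covers adverse events and serious adverse events, and also laboratory changes, vital signs, ECG, LVEF and clinical examinations including skin and eyes. For each endpoint the protocol says: "It will be studied using descriptive statistics techniques, such as frequency tables and contingency tables". Section 10.6 defers full analysis details to the SAP.

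SAP section 5 specifies the safety population and then goes straight to its tables, from "Table 124: Overall safety" to "Table 129: Grade of most frequent AEs with 5% threshold overall", with two patient listings (127, 130) among them. Annex 1 adds one more listing (168). Radiotherapy does define a split elsewhere in the SAP: an appended part has a section headed "OS ON ITT ACCORDING TO RADIOTHERAPY", and the next section does the same for intracranial PFS.

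**The concern.** The protocol separated toxicity before and after local treatment for a stated reason. Section 3 says that combining or sequencing targeted therapy with radiation raises some concern about radionecrosis and dermatitis, and that most of the evidence comes from retrospective series. All-period counts cannot show which events began after radiation. If the SAP is run as it appears, two named secondary endpoints would drop out of the report, even though the analyses do split survival outcomes by radiotherapy.

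**Working it through.** No sample-size or error-rate figure is involved. The check sets the protocol's commitment beside each safety table that can be seen.

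**Step 1. Summary tables in SAP section 5.**

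| Table | What can be read | Local-treatment period shown? |
|---|---|---|
| 124 | Rows for AEs, grade 3 or higher, relatedness to each drug, SAEs; column heads lost, label Cohort survives | None in the rows; columns cannot be read |
| 125 | Toxicity, frequency, percentage | No |
| 126 | Toxicity by grade; title says overall | No |
| 128 | AE, frequency, percentage | No |
| 129 | AE by grade; title says overall | No |

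Result: 0 of the 4 tables with readable columns is split by period, and 1 of the 5 cannot be fully read. The same four tables also show no cohort split, although both objectives are stated for both cohorts.

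**Step 2. Listings.** Tables 127, 130 and 168 are patient listings. Tables 130 and 168 carry AE start dates and Table 127 shows none. None has a visible period column. A listing is not the frequency table that section 10.2 describes.

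**Step 3. Other components.** SAP section 5 shows no table, by period or otherwise, for the laboratory, vital-sign, ECG, LVEF or examination parts of the two endpoints.

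**Step 4. What cannot be seen.** The numbering jumps from 130 to 132 and from 136 to 146. Tables 137 to 145 fall between the corticosteroid section (6.1) and the neurological symptom table (6.2.1), so they are unlikely to be AE tables. Table 131 falls between the last table of section 5 and the first of section 6.1. Its content is unknown, and it is the main uncertainty.

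**Step 5. The interval between the two windows.** The first window ends at day 1 of local treatment and the second opens after the end date. For a multi-fraction course, the days in neither window are the day of the last fraction minus 1, if D1 counts in the first window:

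- Whole-brain course, 10 fractions on weekdays (section 7.1.4.1): a Monday start ends on day 12, so 12 − 1 = 11 days. A Tuesday to Friday start ends on day 14, so 14 − 1 = 13 days.
- Stereotactic, three fractions per week (section 7.1.4.2; Monday, Wednesday, Friday assumed): 3 fractions end on day 5 or 6, giving 4 to 5 days; 5 fractions end on day 10 or 11, giving 9 to 10; 6 fractions end on day 12 or 13, giving 11 to 12.
- Single fraction: 0 days.

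Add one day to each if D1 is excluded. The documents give no mix of schedules and no event counts, so these days cannot be converted into a number of AEs.

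**The case against.** The strongest objection is that the text is incomplete at the critical place. Table 124 has lost its column heads and Table 131, next to the safety section, is not visible. A reader might infer that the SAP omits these endpoints altogether. The documents do not support that: a period split in Table 124's columns is unlikely given the Cohort label but cannot be excluded, and Table 131 could hold anything. The SAP also does not withdraw the tables the protocol prescribes, and Listings 130 and 168 hold AE start dates from which a split could be derived. This objection stands as a limit on the claim. It does not supply the missing output, because no table that can be seen reports either endpoint.

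A second tempting reading is that the interval between the windows is an error that loses radiation-period events. That is not supported either. The endpoints concern toxicity of the drug combination, and sections 5.3 and 7.3.3 hold both drugs from 24 hours before radiotherapy to 24 hours after the last dose. Leaving those days out may well be deliberate, although no section says so. Events in that interval also stay in the overall treatment-emergent summary of section 10.6. What remains is a request for clarification.

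Finally, the endpoints are descriptive and the primary endpoint does not depend on them. That is correct and limits the importance of the point.

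**Conclusion.** The point holds in a limited form. Two secondary endpoints with defined windows and a stated form of presentation have no visible summary output in the SAP: none of the four readable tables is split by period, and the fifth shows no period in what survives of it. Run as shown, the SAP would give all-period counts and leave both endpoints unreported. This should be corrected, but it changes no primary or other efficacy conclusion.

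The conclusion assumes that Table 124's lost columns are cohorts and that Table 131 is not a period-specific safety table. If either assumption is wrong, the point shrinks to the remaining tables and components. The interval between the windows is a minor matter of definition, and the number of AEs it touches is unknown.

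**What to change.** Add to SAP section 5:

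- The AE and SAE summaries, in the form of Tables 124, 125, 126, 128 and 129, for each of the two protocol-defined periods, by cohort and overall. Assign events by onset date, use patients at risk in each period as the denominator, and show time at risk, because the periods differ in length.
- The laboratory, vital-sign, ECG, LVEF and examination components of section 10.2, by the same periods.
- A rule for patients who never receive local radiation: report them as a separate group, or state how they are assigned. The documents do not settle this.

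Present the tables as description and not as a before/after comparison.

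As a minor clarification, state whether events between D1 and the end of a multi-fraction course are left out on purpose or shown in a separate row. Also state how a second local treatment, which section 5.3 allows, is assigned. The end of the second period needs stating too, because section 8.1 collects AEs to the end-of-treatment visit or resolution while section 9 assesses them to the end of the study.

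The cost is a short definition and some re-tabulation of dated AE data, with small counts in some cells. Local-treatment start and end dates must be available. The endpoint definitions presuppose them, although Table 47 shows no date column. The interruptions for local treatment in Tables 33 and 36, with the incidence dates in Tables 34 and 38, can serve as a cross-check. SAP section 3.5 already refers to database closure; if the tables are added after that, label them a late clarification.

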## 7.1.4. Radiation therapy 

## 7.1.4.1 Whole Brain Radiation Therapy

- 1. Total Dose:
  - The whole brain planning target volume (PTV) will receive 30 Gy in 10 fractions.
  - Treatment will be delivered once daily, 5 fractions per week, over 2 to 2.5 weeks.
  - 2. Immobilization, Simulation, Localization:
    - Patients will be treated in the supine position using an adequate immobilization (aquaplast mask).
    - A treatment-planning CT scan of the whole head region must be acquired with the
      patient in the same position and immobilization device as for treatment. Axial slice
      thickness not exceeding 3-5 mm will be required. Contrast IV and MRI-CT fusion are
      not necessary.
  - 3. Target volumes:
    - It is not necessary to define the Gross Tumour Volume (GTV).
    - The Clinical Target Volume (CTV) is defined as the whole brain parenchyma to C1 (if no posterior fossa metastasis) or C2 (if MRI evidence of posterior fossa metastasis).
    - The PTV is defined as the CTV + 0.5 cm with clip at patient surface.
  - 4. Treatment Planning:
    - Treatments must be delivered with 3-D planning through parallel opposed fields that cover the entire cranial contents (also it is allowed static or dynamic intensity modulation).
    - All portals will be treated daily.
    - Treatment will be delivered using megavoltage machines with photon beams ranging from 4 to 8 MV. Electron, particle, or implant therapy is not permissible.

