#### 7.1.4.2. Radiosurgery/Stereotactic radiosurgery

- 1. All participating institutions must use approved stereotactic localization procedures for imaging and treatment delivery.
- 2. Devices: Gamma Knife or Accelerator Linac-Based Systems (IMRT, Rapid Arc, VMAT), Cyberknife, or Tomotherapy Hi-Art system.
- 3. Total Dose:
  - a. Dose selection must be based on previously published Radiation Therapy Oncology Group (RTOG) data, with dose modification left up to the treating physician. The total dose will depend on the size of the metastatic lesion(s) and proximity to critical structures.
  - b. Suggested doses are as follows: 1 fraction x 15-25 Gy; 3 fractions x 9-11 Gy; 5 fractions x 6-7 Gy; or 6 fractions x 5-6 Gy.
  - c. For GTV > 20 mm hypofractionated stereotactic radiotherapy could be prefered.
  - d. Treatment will be delivered once daily, alternate-day, 3 fractions per week.
- 4. Immobilization, Simulation, Localization:
  - a. Patients will be treated in the supine position using an adequate immobilization facemask/stereotactic frame.
  - b. A treatment-planning CT scan of the whole head region must be acquired with the patient in the same position and immobilization device as for treatment. Axial slice thickness not exceeding 2-3 mm will be required to define gross tumour volumes.
  - c. Administration IV contrast increases the diagnostic accuracy of CT.

- d. The MRI planning and treatment-planning CT should be fused.
- 5. Target volumes:
  - a. GTV will be delineated on axial T1-weighted gadolinium-enhanced MRI. Areas of edema will not be considered part of the target volume.
  - b. PTV will be defined as expanding GTV 1-2 mm.
- 6. Treatment Planning:
  - a. Treatments must be delivered with Intensity-Modulated RT. Acceptable IMRT modalities include helical tomotherapy or LINAC-based IMRT involving static gantry angles or volumetric arc therapy (VMAT). It is also possible to use Gamma Knife.
- 7. Dose Specification:
  - a. The Dose will be prescribed to the isodose surface (50-90% [maximum = 100%]), which encompasses the target, to ensure at least 95% coverage of the PTV with the prescription dose. The 100% (maximum) dose and minimum dose will be recorded for each patient.
  - b. Three isodose lines should be submitted: the prescription isodose line, 90% of the prescription isodose line (not 90% of total dose) and 80% of the prescription isodose line.
    - Acceptable variation: 80% isodose line covers the target

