#### 7.3.3. Prohibited concomitant treatment

Any other investigational treatment within the past 30 days of treatment initiation and during the trial is disallowed.

Anticancer therapies (including chemo- or biologic-therapy or radiation therapy, covering >30% of the red bone marrow reserve, and surgery) are prohibited while the patients are receiving study treatment. If such therapeutic measures are required for a patient, then the patient must be discontinued from study treatment. If local treatment, radiotherapy or surgery, is indicated by the protocol of this study, it is allowed but following the next indication regarding the study treatment. To reduce possible skin toxicity during and after radiotherapy, encorafenib and binimetinib will be interrupted 24h before radiotherapy and restart 24h after the last dose of radiotherapy.

The concomitant use of strong CYP3A4 inhibitors would likely significantly increase the exposure of encorafenib and thus should not be used during this study.

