#### 10.6. Statistical analysis

For each categorical variable, the results will be summarized by frequencies and percentages. For each continuous variable, the results will be summarized by descriptive statistics such as median, range, and interquartile range or by means, standard deviations and 95% confidence intervals (CIs). For proportions, point estimates and exact 95% confidence intervals will be calculated. For time to event endpoints, Kaplan-Meier estimates at selected time points and corresponding curves will be presented. Time to event is derived relative to the first study treatment administration. Laboratory values will be expressed as the absolute values and as grading (ordinal categorical variables) according to NCI CTCAE v 4.03.

Treatment-emergent AE (AEs starting after the administration of study treatment and up to study completion) will be summarized by system organ class and preferred term. Grading will be presented by type and grade in tables showing frequency and percentage of the within-patient worst grades. In addition, grade ≥3 AEs will be summarized separately. Full analysis details will be outlined in the statistical analysis plan (SAP).

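### The two toxicity windows in Protocol 10.2 leave the days of fractionated local treatment in neither secondary safety endpoint

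*Combined protocol and SAP*

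**What the plan says.** The Synopsis and Protocol 4.2 list two toxicity objectives for each cohort: toxicity of the drug combination up to local treatment, and toxicity of the combination after it. Protocol 10.2 gives the limits. The first endpoint counts adverse events, serious adverse events and changes in safety measurements "until local treatment (local treatment D1". The second counts the same items "after local treatment (after end of local treatment date".

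Local treatment may last more than one day. For whole brain radiotherapy, Protocol 7.1.4.1 states: "The whole brain planning target volume (PTV) will receive 30 Gy in 10 fractions", and "Treatment will be delivered once daily, 5 fractions per week, over 2 to 2.5 weeks". For radiosurgery, Protocol 7.1.4.2 suggests "1 fraction x 15-25 Gy; 3 fractions x 9-11 Gy; 5 fractions x 6-7 Gy; or 6 fractions x 5-6 Gy", with the schedule "Treatment will be delivered once daily, alternate-day, 3 fractions per week".

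Both drugs are stopped 24 hours before radiotherapy and restarted 24 hours after its last dose (Protocol 5.3 and 7.3.3). Protocol 7.3.3 gives the reason: "To reduce possible skin toxicity during and after radiotherapy". Separately, Protocol 10.6 plans an overall summary of events defined as "Treatment-emergent AE (AEs starting after the administration of study treatment and up to study completion". The tables in SAP section 5 have no split around local treatment.

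**The concern.** Two endpoints named as before and after local treatment look as if they divide the safety follow-up of an irradiated patient. They do not: the first stops at the first day of local treatment and the second opens only once local treatment has ended. The protocol itself names skin toxicity during radiotherapy as something to guard against, and its rationale (section 3) mentions radionecrosis and dermatitis when targeted therapy is combined or sequenced with radiation. A programmer who follows 10.2 literally would nevertheless leave an acute event during a course of radiotherapy out of both endpoints. A reader who adds the two together would take the result as the full toxicity experience around local treatment, which it would not be.

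**Working it through.** **Limits side by side.** Window 1 ends at day 1 (D1) of local treatment; the text does not say whether D1 itself is inside. Window 2 begins after the end date. For an event that starts after D1 and no later than the end date:

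- If it resolves by the end date, it is in neither window, whether events are assigned by onset or by presence.
- If it persists beyond the end date and events are assigned by onset, it is in neither window.
- If it persists and events are assigned by presence, it is in window 2.

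Protocol 10.2 and SAP section 5 do not say which assignment rule applies.

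**The plan's own duration.** 10 fractions / 5 per week = 2.0 weeks, which matches the lower end of the stated 2 to 2.5 weeks. The upper end is 2.5 × 7 = 17.5, or about 17 whole days.

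**Length of the gap.** Let L be the calendar days from D1 to the last fraction, both included. The uncovered days are L − 1 if D1 belongs to window 1, and L if it does not. I assume no breaks, weekday delivery for whole brain treatment, and Monday-Wednesday-Friday delivery for stereotactic treatment. The ranges for L come from varying the starting weekday.

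| Local treatment | L | Gap, D1 in window 1 | Gap, D1 not in window 1 |
|---|---|---|---|
| Whole brain, 10 fractions at 5 per week | 12-14 | 11-13 | 12-14 |
| Whole brain at the stated 2.5 weeks | about 17 | about 16 | about 17 |
| Stereotactic, 3 fractions | 5-6 | 4-5 | 5-6 |
| Stereotactic, 5 fractions | 10-11 | 9-10 | 10-11 |
| Stereotactic, 6 fractions | 12-13 | 11-12 | 12-13 |
| Single fraction | 1 | 0 | 1 |

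For example, ten fractions starting on a Monday end on the Friday of the following week, so L = 12. Any other weekday start takes in a second weekend, so L = 14.

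**Does another part of the plan close the gap?** No. The overall summary in Protocol 10.6 and the tables in SAP section 5 do include these events, but undivided in time. SAP section 5 contains no table for either window, so it neither implements the two endpoints nor settles where the intervening days go.

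**A second undefined date.** The Synopsis and Protocol 5.3 allow further local treatments after the first. The end date that opens window 2 may then not be a single date.

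**The case against.** The strongest defence is that both endpoints concern toxicity of the combination, and both drugs are interrupted on the uncovered days. Leaving off-drug days out of two on-drug windows would be a reasonable choice. That has force, and it argues against simply merging the radiotherapy days into the second window. It does not remove the problem: the protocol never gives this as the reason, the second endpoint is not restricted to events on drug, and the interruption starts only 24 hours before radiotherapy in patients due to have had 56 days of treatment before the first assessment.

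It is also true that nothing is lost from the database. Events are collected from consent to the end-of-treatment visit and enter the overall tables, and the SAP listings of serious adverse events and of all toxicities carry start and stop dates. What is missing is the breakdown around local treatment.

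A reader might infer three stronger conclusions that the documents do not support:

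- *The three-patient running phase is compromised.* It uses its own criteria in Protocol 5.3 (deterioration in vital signs including performance status, physical examination, ECG and laboratory values), not the windows of 10.2.
- *The after-treatment rate is biased low.* A rate defined as starting after the end date is not biased because it omits earlier days. The documents do not show that the omitted days carry the most interaction toxicity; the skin concern covers both during and after radiotherapy.
- *Comparisons by radiation technique are distorted.* The gap does vary by technique, but no safety comparison by technique is planned. The SAP gives radiotherapy frequencies, and its only radiotherapy contrasts are overall survival and intracranial progression-free survival, with versus without radiotherapy.

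**Conclusion.** The point holds as a narrow defect of definition in two descriptive secondary endpoints. Under the stated limits, events that start and resolve during fractionated local treatment belong to neither endpoint; events that start then and persist also belong to neither if assignment is by onset. The uncovered interval is about 11-14 days for whole brain treatment (up to about 17 at 2.5 weeks), about 4-13 days for three to six stereotactic fractions, and 0-1 day for a single fraction. These counts assume delivery without breaks on the weekdays given above, and the ranges cover both readings of D1. The number of events affected cannot be derived from the documents. The primary endpoint and the overall safety summary are not affected.

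**What to change.** In Protocol 10.2 and the SAP:

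1. End the first period on the day before D1 of the first local treatment.
2. Report D1 to the end date (or to drug restart) as a separate row for the period during local treatment, shown next to the after-treatment period and also combined with it. Off-drug radiotherapy toxicity then stays visible without being merged into the after-treatment figure.
3. Assign each event by onset date, and count a grade increase in the period in which it occurs.
4. State which start and end dates apply when local treatment is repeated.
5. Add these split tables to SAP section 5, which now has none for either endpoint.

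The periods then leave no uncovered day under any technique. The cost is a few sentences, one derived variable and some extra descriptive tables. No new data are needed: event start and stop dates already appear in the SAP listings, and the current endpoint definitions already require the start and end dates of local treatment. No dose or clinical rule changes.

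### No visible SAP safety table splits adverse events at local treatment, and the protocol's two toxicity windows leave out events that start during a multi-fraction course

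*Combined protocol and SAP*

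**What the plan says.** **Endpoints.** The Synopsis and protocol 4.2 list toxicity up to local treatment as a secondary objective, and with it "Toxicity of the combination after local treatment in both cohorts". Protocol 10.2 defines each as its own endpoint (adverse events, serious adverse events, laboratory and other examinations, CTCAE-graded), to be described with frequency and contingency tables. The first is counted "until local treatment (local treatment D1", the second "after local treatment (after end of local treatment date". Protocol 10.6 leaves the full analysis detail to the SAP.

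**Course length.** Whole brain radiotherapy (WBRT) is 30 Gy in 10 fractions (7.1.4.1): "Treatment will be delivered once daily, 5 fractions per week, over 2 to 2.5 weeks". For radiosurgery, 7.1.4.2 suggests 1, 3, 5 or 6 fractions: "Treatment will be delivered once daily, alternate-day, 3 fractions per week". Under 7.3.3 both drugs are held from 24 hours before radiotherapy until 24 hours after its last dose.

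**SAP.** Section 5 is set in the safety population. Its visible tables sort events by relatedness (for example "Toxicity: AE related to any treatment"), grade ("List of toxicities grade >=3 in all patients"), frequency ("Most frequent AEs with 5% threshold"), seriousness and cohort. Tables 45-47 describe who was irradiated, and the supplementary tables (2.2 and 2.3) split overall survival and intracranial PFS by radiotherapy.

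**The concern.** Giving targeted therapy first and radiation second is the core of this design: patients with neither complete response nor progression at the first assessment are irradiated by protocol. Section 3 names radionecrosis and increased dermatitis as concerns with such combinations. The first three irradiated patients form a running phase, and the drugs are paused to limit skin toxicity. Toxicity after local treatment is therefore a safety question the trial itself raises.

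Two things stand in the way of answering it. The SAP shells show one overall count, which mixes events before and after local treatment and patients with and without it. And even if the split were programmed exactly as 10.2 is written, events that begin during a fractionated course would count toward neither endpoint.

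**Working it through.** **Step 1. Do the visible tables carry the split?**

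| SAP table | Organised by | Period or local-treatment split |
|---|---|---|
| 124 | Any AE, grade, relatedness, SAE, by cohort | No |
| 125, 126 | Toxicity by term; by term and grade (5% threshold) | No |
| 127 | Listing of toxicities of grade 3 or higher | No |
| 128, 129 | AE by term; by term and grade (5% threshold) | No |
| 130 | Listing of SAEs with start and stop dates | No |

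That is 0 of 7. The Annex listing (Table 168) has AE start and stop dates but no period column either. The supplementary tables use radiotherapy as a grouping factor for survival and intracranial PFS only.

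**Step 2. Do the two windows meet?** Window 1 ends at D1. Window 2 starts after the end date. Reading D1 as inside window 1, the days in neither are

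uncovered days = (date of last fraction) − (date of first fraction).

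This is zero only when the course is a single fraction.

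**Step 3. How long is the gap?** The plan's own course length reproduces: 10 fractions at 5 per week is 10/5 = 2 weeks, the lower end of its stated range. The count below assumes no missed fractions, weekday delivery for WBRT, and Monday/Wednesday/Friday for radiosurgery. It runs over every possible starting weekday.

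- WBRT, 10 fractions: Monday start to Friday of week 2 = 11 days; any other start crosses a second weekend = 13 days. Result: 11-13.
- WBRT at the stated upper limit: 2.5 × 7 − 1 = 16.5, so about 16 days.
- Radiosurgery, 3 fractions: Monday to Friday = 4; Wednesday to Monday = 5. Result: 4-5.
- Radiosurgery, 5 fractions: Monday to Wednesday of the next week = 9; Friday to the second Monday = 10. Result: 9-10.
- Radiosurgery, 6 fractions: Monday to Friday of the next week = 11; Wednesday to the second Monday = 12. Result: 11-12.
- Radiosurgery, 1 fraction: 0.

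**Step 4. Does the drug pause explain the gap?** The pause begins 24 hours before radiotherapy, inside window 1, and ends 24 hours after the last dose, inside window 2. The uncovered interval lies between. Each window already contains off-drug time, so the windows were not drawn to exclude the pause.

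**The case against.** **Table 131 cannot be seen.** Section 5 ends visibly at Table 130 and section 6.1 opens with Table 132, so a further safety table may sit exactly there. Several shells, and the header of Table 47, are also damaged in extraction. This stands. The claim is about visible tables only, and nothing should rest on what Table 47 seems to lack.

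**The endpoints are still prespecified.** Protocol 10.2 names both periods and the method, and omitting them from a set of shells does not cancel that. This is fair, but 10.6 hands the detail to the SAP, and a programmer following these shells would not produce the split.

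**The gap may be intended or harmless.** The endpoint is toxicity of the drug combination, and the drugs are off during radiotherapy. Protocol 10.2 also gives no onset rule, so an event that starts in the course and persists might be counted as after. The first argument fails at step 4 of the working, and the documents state no such intention. On the second, 10.6 defines treatment-emergent events by their start, which makes onset the natural reading; if persistence is meant to count, 10.2 should say so.

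**The size is in days, not patients.** This stands. The documents give no number irradiated and no event count, and the radiosurgery schedules are suggestions that the treating physician may modify. Nothing in the documents shows that radionecrosis or dermatitis would begin in the uncovered days.

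**Conclusion.** The point holds at moderate weight. Two secondary safety endpoints have no visible home in the SAP as defined, and their windows leave 4-13 days uncovered for multi-fraction courses on the plain schedules, up to about 16 for a slow WBRT course. This assumes that events are assigned by onset, that D1 belongs to the first window, and that no fractions are missed. The primary result is unaffected.

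Three stronger readings are tempting and are not supported:

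- *Events during radiotherapy go unreported.* They still enter the overall tables, and serious ones enter Table 130.
- *The SAP breaks the protocol's promise on grade 3 or higher events.* Protocol 10.6 asks for a separate summary of these, not one by term, and Table 124 has an all-cause grade 3 or higher row.
- *Table 168 omits unrelated events.* Its scope cannot be told from the text available.

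The 5% threshold and the absence of a system organ class level in Tables 128-129, set against the summary described in 10.6, are at most a minor note. If the pooled safety population equals the planned 63, a term seen in 3 patients (3/63 = 4.8%) would not be named there, and one seen in 4 (4/63 = 6.3%) would.

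**What to change.** In SAP section 5, present the AE and SAE summaries (any, grade 3 or higher, related, by term and worst grade) by period of onset, for each cohort and pooled:

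- (a) first dose to D1 of the first local treatment, in the safety population;
- (b) the day after D1 to the end date of local treatment, shown as its own window with a note that study drugs are paused, or merged into (c);
- (c) after the end date.

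Use patients who received local treatment as the denominator for (b) and (c). Irradiated patients alone would be too narrow, because 7.3.3 counts surgery as local treatment too. Section 5.3 allows further local treatments, so assign repeat courses by the first course. State also that patients who never receive local treatment contribute only to (a), which 10.2 does not say.

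Amend protocol 10.2 so that the windows meet without overlapping: D1 stays in (a), and the next window begins the following day. Starting the second window on D1 itself would count that day twice. With this change the gap is zero for every schedule.

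The cost is longer tables and a short protocol wording change. AE start dates (Tables 130 and 168), radiotherapy status (Tables 45-47) and drug interruptions for local treatment (Tables 33-38) already appear in the SAP, so no new data collection is expected, provided that local treatment start and end dates are in the database.
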